- VS, Part 2: Taken immediately before infusion (approximately 10 minutes prior to start of infusion); at 15, 30, and 60 minutes after the start of infusion; at end of infusion; and following the infusion, every 15 minutes up to 60 minutes, then every 60 minutes up to 6 hours after the completion of first infusion and up to 4 hours for subsequent infusions.
- Blood samples for PK, PD, and cytokine release per [Appendix 1](#) and [Appendix 2](#).
- ECG: Perform 2 ECGs after the infusion is completed; 1) within 30 minutes of end of infusion and 2) 60 minutes after infusion.

In Part 1, the study coordinator will see participants at 24- and 48-hours post-infusion (± 5 hours). Contact will be maintained for follow-up of complications and other participant concerns that arise during this time.

In Part 2, the study coordinator will see participants at 24-hours post-infusion (± 5 hours) and on Day 3. Telephone or contact participants via their preferred way of communication for study visits conducted remotely after infusion to inquire about any reactions or potential treatment emergent adverse events (TEAEs). Participants will be instructed to contact the study coordinator or Investigator if any signs or symptoms of an AE occur not only after the infusions but at any time during the study.

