17 Pre-MGD014 Infusion Medications (Diphenhydramine or equivalent H1-antihistamine and Acetaminophen) and other medications administered for hypersensitivity Anaphylactic Reaction:

- a. Diphenhydramine (IV) or equivalent H1-antihistamine and the Acetaminophen (oral) administered by licensed study staff.
- b. Administration of medications for treatment of adverse reactions to the MGD014 will follow hospital policy and the UNC HIV Cure Center SOP entitled “DART Infusion Guidelines and Emergency Management Plan”.

18 Post-Infusion Assessment: Participants provided with instructions to contact study staff about any reactions that occur after receipt of MGD014. Part 1 participants will return to the clinic on Days 1 and 2. Part 2 participants will return for Day 3 assessment and for post-infusion Day 14 and Day 28 to be contacted approximately 2 to 3 days after the study drug administration to inquire about reactions or any potential treatment emergent adverse events (TEAEs). Infusion reactions graded per the DAIDS Toxicity Table.

19 Chemistry: Na, K, Cl, bicarbonate, BUN, creatinine, glucose, Ca, total protein, AST, ALT, alkaline phosphatase, total bilirubin, and Mg. Indirect bilirubin required if participant on atazanavir. Clinical labs scheduled for the day of infusion (this is inclusive of CBC) can be obtained within 7 days of infusion.

20 Pregnancy test: Serum pregnancy test done on all women at screening. Urine pregnancy test/POCT done on all women at or within 72 hours of each infusion. Test results must be negative, documented and reviewed by study PI or designee prior to each infusion.

21 For ADA, PK, PD, RO, Serum Cytokine, and T Cell Phenotype measurements, please refer to [Appendix 2](#) for detailed schedule.

22 CBC done for leukapheresis procedure only.

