Note: Actual start and end of infusion times, PK, and ADA sample collection times will be recorded on the source documents. All sample time points are hours after EOI, unless otherwise specified. Samples required at EOI can be drawn up to 5 minutes before the infusion is complete, post EOI samples can be drawn +/- 5 minutes; duration of infusion = 120 minutes. 24 - and 48-hour samples will be drawn on Day 1 and 2 respectively.

Abbreviations: ADA = Anti-drug antibody; EOI = end of infusion; PK = Pharmacokinetic.

PART 2 Pharmacokinetics, Immunogenicity, and Pharmacodynamic Biomarkers Blood Sampling Schedule for MGD014						
MGD014 Dosing	Treatment Day	PK ^a Sampling Time (Hours)	ADA Sampling Time (Hours)	Receptor Occupancy ^b (Hours)	Serum Cytokines ^c (Hours)	T cell Phenotype (Hours)
X	0	0 ^d (Pre-infusion)		0 ^d (Pre-infusion)	0 ^d (Pre-infusion)	0 ^d (Pre-infusion)
	0	EOI				
	0	1 (post EOI)				
	0	4 (post EOI)		4 (post EOI)	4 (post EOI)	4 (post EOI)
	1	24 +/- 5 hours (post EOI)		24 +/- 5 hours (post EOI)	24 +/- 5 hours (post EOI)	24 +/- 5 hours (post EOI)
	3	72 +/- 5 hours (post EOI)			72 +/- 5 hours (post EOI)	
X	14	0 (Pre-infusion)	0 (Pre-infusion)	0 (Pre-infusion)		0 (Pre-infusion)
	14	EOI		4 (post EOI)	4 (post EOI)	4 (post EOI)
X	28	0 (Pre-infusion)	0 (Pre-infusion)	0 (Pre-infusion)		0 (Pre-infusion)
	28	EOI		4 (post EOI)	4 (post EOI)	4 (post EOI)
	42	1008 hours +/- 1 day				
	77 (EOS visit)	1848 hours +/- 3 days	X	X		X

- a Do not collect PK samples from infusion port. Obtain PK samples as follows: Pre-infusion: Before start of infusion on visit day (dosing day) or day before. When collecting multiple samples, collect the PK sample first.
- b If at any time in Step 3 RO reaches below the limit of detection, at the discretion of the PI or designee, further measurement of RO may be deemed unnecessary.
- c Additional samples may be obtained selectively at additional time points in participants who experience signs and symptoms of cytokine release.
- d All pre-dose PK, ADA, Receptor Occupancy including T-cell binding, cytokines, and T-cell Phenotype samples will be collected prior to start of MGD014 infusion; the start of MGD014 infusion is designated as time = 0 hour.

Abbreviations: ADA = Anti-drug antibody; EOI = end of infusion; PK = Pharmacokinetic.

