Note: Actual start and end of infusion times, PK, and ADA sample collection times will be recorded on the source documentation. All sample time points are hours after EOI, unless otherwise specified. Samples required at EOI can be drawn up to 5 minutes before the infusion is complete, post EOI and 4 hr post EOI samples can be collected +/- 5 minutes; duration of infusion = 120 minutes. 24- and 72-hour samples will be drawn on Day 2 and 4, respectively.

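### The note under the Part 2 sampling table in Appendix 2 puts the 24-h and 72-h samples on Days 2 and 4, while the table and visit schedule put them on Days 1 and 3

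*Protocol*

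**What the plan says.** Five places in the protocol bear on when the early Part 2 samples are taken.

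- **Appendix 2, Part 2 note:** "24- and 72-hour samples will be drawn on Day 2 and 4, respectively".
- **Appendix 2, Part 2 table:** the first infusion is on Treatment Day 0. The row for Day 1 carries "24 +/- 5 hours (post EOI" for PK, receptor occupancy, cytokines and T-cell phenotype. The row for Day 3 carries "72 +/- 5 hours (post EOI" for PK and cytokines.
- **Appendix 1, Part 2:** visits are listed for Days 0, 1, 3 and 14, with a window of 0 for Days 1 and 3. There is no Day 2 or Day 4 visit.
- **Section 6.6.3:** "In Part 2, the study coordinator will see participants at 24-hours post-infusion (± 5 hours) and on Day 3".
- **Appendix 1, footnote 18:** "Part 2 participants will return for Day 3 assessment".

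The matching note for Part 1 reads "24 - and 48-hour samples will be drawn on Day 1 and 2 respectively", which agrees with an infusion on Day 0.

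On the time origin, the Part 2 note says "All sample time points are hours after EOI, unless otherwise specified". Footnote d to the same table sets the start of infusion as hour 0. The Day 42 PK cell reads "1008 hours +/- 1 day" and the Day 77 cell gives 1848 hours. Unlike the 1-, 4-, 24- and 72-h cells, neither is marked as post EOI.

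**The concern.** The note is a sampling instruction, and it contradicts the table it belongs to. The 24-h and 72-h draws are the only scheduled PK samples between 4 h after the first infusion and Day 14. They are also the only scheduled cytokine samples between 4 h after the first infusion and 4 h after the second. The 24-h draw is the only receptor occupancy and T-cell phenotype sample between 4 h and the Day 14 pre-infusion sample.

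PK and serum cytokines are secondary objectives, and both documents plan to tabulate cytokines by time (Protocol 14.7.1, SAP 4.11.1). A draw made a day late leaves a hole in the early profile and, if filed under its nominal label, puts a roughly 48-h value in the 24-h column.

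The late PK rows raise a lesser question. Their hours do not follow the note's default, and the PK column restarts at 0 on Days 14 and 28, so the reader is not told which clock applies.

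**Working it through.** **Inputs (all from the protocol).** First infusion on Day 0, last on Day 28; infusion lasts 2 h; windows are 24 ± 5 h (19 to 29 h) and 72 ± 5 h (67 to 77 h) after EOI.

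**1. Day numbering.** If Day 0 is the infusion day, day d at the clock time of infusion start is 24d h from start and 24d − 2 h from EOI. For Part 1 Days 7, 14, 21, 28 and 42 this gives 166, 334, 502, 670 and 1006 h, which are the hours printed in the Part 1 table.

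**2. The table's placement in Part 2.** Day 1: 24 × 1 − 2 = 22 h after EOI, inside 19 to 29 h. Day 3: 24 × 3 − 2 = 70 h, inside 67 to 77 h. The table agrees with itself.

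**3. The note's placement.**

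| Sample | Day in note | Hours after EOI | Window closes | Excess |
|---|---|---|---|---|
| 24 h | 2 | 24 × 2 − 2 = 46 | 29 | 46 − 29 = 17 h |
| 72 h | 4 | 24 × 4 − 2 = 94 | 77 | 94 − 77 = 17 h |

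If the sample is instead taken at the clock time of EOI, the hours are 48 and 96 and the excess is 19 h.

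**4. Could a draw early on Day 2 or Day 4 still be in window?** Let EOI fall c hours after midnight on Day 0. The 24-h window closes at c + 29 and Day 2 begins at hour 48, so they overlap only if c ≥ 19. The 72-h window closes at c + 77 and Day 4 begins at hour 96, so again c ≥ 19. The note can be met within window only if the infusion ends at 19:00 or later.

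**5. Another numbering.** If the infusion day were Day 1, Days 2 and 4 would be (2 − 1) × 24 = 24 h and (4 − 1) × 24 = 72 h. That would explain the note, but the protocol numbers the infusion day as Day 0 throughout.

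**6. Late PK rows.** From the start of the first infusion: 42 × 24 = 1008 and 77 × 24 = 1848, exactly as printed. From EOI of that infusion: 1006 and 1846, a difference of 2 h against windows of ±1 and ±3 days. From EOI of the Day 28 infusion: (42 − 28) × 24 − 2 = 334 and (77 − 28) × 24 − 2 = 1174.

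**The case against.** The best case on the other side is that this is editorial. Days 1 and 3 can be read from the table, the visit schedule, Section 6.6.3 and footnote 18. Following the note would need two visits that the schedule does not contain. The note still calls the draws 24-h and 72-h samples, and actual collection times must be recorded (Sections 9.13 and 9.15), so a late draw would be visible.

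Most of this stands as an argument that the error is unlikely to be carried out and unlikely to go unnoticed. It does not make the note right. Recording the true time allows correct analysis of what was drawn, but it does not supply the sample that was missed.

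A reader might go further and infer that 1008 h and 1848 h are counted from the wrong infusion, and should be 334 h and 1174 h. The documents do not support that. Both figures are exact from the start of the first infusion, match the Treatment Day printed in their rows, and agree with footnote d. No passage requires late samples to be timed from the Day 28 EOI. Part 1 cannot settle it, because with a single infusion the first and the preceding EOI are the same. Nor does any passage plan a PK analysis on these nominal hours as time since the third dose.

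**Conclusion.** The contradiction is established: the Part 2 note disagrees with its own table and with three other places in the protocol. If followed, it puts the 24-h and 72-h samples about one day late, nominally 17 h outside their windows. That figure assumes sampling at the clock time of infusion start. The conclusion that the draws miss their windows holds for any infusion ending before 19:00 on Day 0.

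The consequence is confined to early PK, receptor occupancy, cytokine and T-cell phenotype data after the first Part 2 infusion, in at most six participants. It does not touch the Part 1 schedule or any planned test.

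For the Day 42 and Day 77 PK cells, what remains is an unstated time origin that departs from the note's hours-after-EOI default by 2 h. It is a labelling gap and not an arithmetic error.

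**What to change.** Change the last sentence of the Part 2 note to Day 1 and Day 3, so that it agrees with the table and the visit schedule. Label the Day 42 and Day 77 PK cells as hours from start of first infusion. Make the same corrections in the laboratory manual if it repeats these entries.

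If Part 2 sampling has already begun, compare the recorded collection times with the ±5 h windows and report any sample outside them under its actual time.

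The cost is one sentence and two table cells. No visit, sample or analysis is added.

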SCA	single copy assay
SD	standard deviation
SOC	system organ class
SOP	standard operating procedure

SPP	statistical programming plan
TLFs	tables, listings, and figures
T_{max}	time to maximal concentration
V_{ss}	steady-state volume of distribution

1 INTRODUCTION

This statistical analysis plan (SAP) provides a detailed and comprehensive description for the analysis of the study CP-MGD014-01 entitled “A Phase 1 Study to Evaluate the Safety, Immunologic, and Virologic Responses of MGD014 Therapy in HIV-Infected Individuals on Suppressive Antiretroviral Therapy”. This SAP Version 1.0 applies to the Protocol [REDACTED] of this study and describes in detail the statistical methods to be used for analysis of the primary, secondary, and exploratory objectives to be collected from this study.

2 STUDY OBJECTIVES

2.1 Primary Objectives

The objective of this study is to characterize the safety and tolerability of MGD014 administered IV to persons living with human immunodeficiency virus-1 (HIV-1) (PLWH) maintained on suppressive antiretroviral therapy (ART).

2.2 Secondary Objectives

- Assessment of pharmacokinetics (PK) and immunogenicity (ADA) of MGD014.
- Assessment of serum cytokine levels following MGD014 administration.

2.3 Exploratory Objectives

- Explore the impact of MGD014 administration on the immunologic response to HIV-1.
- Explore correlations between virologic and immunologic responses to MGD014.
- Assess the ability of MGD014 to alter markers of persistent HIV-1 infection.

The results of exploratory objectives may not be included in the clinical study report (CSR) or database lock unless they represent meaningful findings.

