3.3 Exploratory Objectives

- Explore the impact of MGD014 administration on the immunologic response to HIV.
- Explore correlations between virologic and immunologic responses to MGD014.
- Assess the ability of MGD014 to alter markers of persistent HIV-1 infection.

The results of exploratory objectives may not be included in the clinical study report (CSR) or database lock unless they represent meaningful findings.

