14.11 Final Analysis

Final analysis of all data will be carried out at the End of the Study.

15 **QUALITY CONTROL AND ASSURANCE**

Quality review activities will be undertaken to ensure accurate, complete, and reliable data. MacroGenics Inc. or designees will do the following:

- Provide instructional material to the study site, as appropriate.
- Sponsor a start-up training session (Investigator Meeting or Study Initiation Visit) to instruct the Investigator and study coordinators. This session will give instruction on the protocol, and study procedures.
- Make periodic visits to the study site to monitor protocol compliance and general Good Clinical Practice (GCP) compliance.
- Be available for consultation and stay in contact with the study site personnel by mail, e-mail, telephone, and/or fax.
- Conduct a quality review of the database.

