4.9 Efficacy Endpoints and Analyses

The following efficacy endpoints are exploratory and only apply to Part 2 patients. The described analyses of these endpoints below are optional and may not be performed if less than 6 patients are eventually enrolled to Part 2.

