4.9.1 Quantitative Viral Outgrowth Assay

For participants who completed the optional leukapheresis, a comparison of pre-MGD014 and post-MGD014 frequency of HIV infection per million resting CD4 T cells will be

performed using a non-parametric 2-sided exact sign test to assess whether or not a significant decrease of infectious units per million (IUPM) CD4 T cells is observed. The primary comparison will be between the leukapheresis taken at baseline and approximately 2 weeks following the last MGD014 infusion in Part 2 (at Day 42 ± 2 weeks). The sign test used for this analysis makes minimal statistical assumptions and is based solely upon whether each participant is observed to have a decrease in IUPM following MGD014 treatment. Results will be presented as the proportion with decreased IUPM and the corresponding confidence interval (CI). If the observed proportion with decreased IUPM is 100% (6/6 participants), the corresponding 95% CI will span from [0.541, 1.000]; this CI would exclude a null hypothesis of no change (H_0 : probability of decrease=0.50).

Table 1 Precision calculations for QVOA analysis

Number of participants with decrease in IUPM	Binomial 95% CI (Clopper-Pearson)
6 of 6 (100%)	[0.541, 1.000]
5 of 6 (83%)	[0.359, 0.996]

IUPM=infectious units per million CI=confidence interval

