4.9.3 Exploratory Endpoints and Analyses

Additional exploratory endpoints are defined as changes in quantitative measures from baseline to post-MGD014 administration. Using a two-sided 0.05 significance level, 10,000 empirical simulations from a normal distribution with mean change equal to 2 standard deviations (SD) with n=6 evaluable participants achieved 86% power to detect a statistically significant change from baseline to post-infusion using an exact Wilcoxon signed-rank test (for paired data). Observed virologic and immunologic measurements may not be normally distributed or may be partially censored due to assay limits of quantification. A Wilcoxon signed-rank test will be used for continuous outcome measures when appropriate; otherwise, an exact sign test will be utilized. Potential immune correlates of antiviral impact will be

assessed graphically (e.g., scatter plots, correlate heat map) and estimated with a non-parametric rank based correlation method. Additionally, association between antiviral impact of MGD014 and baseline participant clinical characteristics, such as stage of HIV infection (acute vs. chronic) at initiation of ART, will also be described and examined. Correlation including one or more measures from the same participant may be assessed using Kendall's tau for clustered data [1]. Exploratory analyses will be conducted using a two-sided 0.05 significance level with no adjustment for multiplicity.

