4.11 Pharmacodynamic Endpoints and Analyses

Summary statistics for biomarkers, such as but not limited to those listed under **CP-MGD014-01 Protocol Section 10.3** and corresponding changes from baseline, will be summarized and may also be presented graphically as will possible associations between changes in PD measures of interest and MGD014 dose and exposure.

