5 LIST OF TABLES, LISTINGS AND FIGURES

The list of tables, listings, and figures (TLFs) and associated shells planned for the clinical study report based on the analyses described in **Section 4.1 - 4.3** of this SAP will be provided in a SPP, which will also include data reporting conventions and programming specifications for the development of these TLFs. The analyses described in **Section 4.4 - 4.6** of this SAP will be performed and presented separately by MG's research group.

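### Whether exploratory results enter the CSR or the database lock may depend on what they show, under a criterion that neither document defines

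*SAP*

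**What the plan says.** SAP 2.3 lists the exploratory objectives and closes with: "The results of exploratory objectives may not be included in the clinical study report (CSR) or database lock unless they represent meaningful findings". Protocol 3.3 ends with the same condition, "unless they represent meaningful findings". I found no definition of the term in either document, and no named decision-maker or time of decision.

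The rule has wide reach. The third exploratory objective concerns markers of persistent HIV-1 infection, which are measured by QVOA and SCA. SAP 4.9 confirms their status: "The following efficacy endpoints are exploratory and only apply to Part 2 patients". SAP 4.9.3 adds further change-from-baseline endpoints, immune correlates and associations with baseline characteristics, without listing them. On error control it says: "Exploratory analyses will be conducted using a two-sided 0.05 significance level with no adjustment for multiplicity".

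Three other places bear on the point:

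- SAP 4.9 makes these analyses optional if fewer than 6 participants enter Part 2. That condition turns on enrolment.
- Protocol 14.11 says: "Final analysis of all data will be carried out at the End of the Study". Protocol 4.5.1 ties the end of the study to database lock.
- SAP 5 says that certain analyses "will be performed and presented separately by" the sponsor's research group, and cites Sections 4.4 to 4.6 for them.

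**The concern.** A reporting rule should depend on things that carry no information about the effect, such as enrolment, assay completion or sample quality. This one depends on the result. If it is used, the exploratory results in the CSR are a selected set, their estimated changes tend to be too large, and null or mixed results need not stand beside them.

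The mention of the lock adds to this. To decide that a result is not meaningful enough to be locked, someone must look at it before lock. Data left out for that reason also sit uneasily with a final analysis said to cover all data.

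The risk differs by endpoint. QVOA and SCA appear in the schedule of events, so a reader could notice their absence. The SAP 4.9.3 endpoints and correlates are not listed, so from these two documents a reader could not tell how many were examined and dropped.

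**Working it through.** **The plan's own figures.** For QVOA with 6 of 6 decreased, the Clopper-Pearson lower limit is 0.025^(1/6) = 0.541, as stated. For 5 of 6 the interval is [0.359, 0.996], also as stated. At n = 6 the exact two-sided sign and signed-rank tests reach p<0.05 only when all six changes share a sign: p = 2/64 = 0.031. The next signed-rank value is 4/64 = 0.0625, and the sign test at 5 of 6 gives 14/64 = 0.219. Power at a mean change of 2 SD is therefore Phi(2)^6 + Phi(-2)^6 = 0.871, against 86% in SAP 4.9.3. The figures reproduce.

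**Assumptions for the illustration, none of them in the documents.** There are six evaluable pairs, and changes are normal with true mean d in SD units. Results that are not meaningful are always omitted. Meaningful is taken in two ways: p<0.05 (strict), or at least 5 of 6 changes in one direction (loose).

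**Strict reading.**

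- Chance of being reported: Phi(d)^6 + Phi(-d)^6.
- At d = 0, each change in a reported set is half-normal, so the mean absolute change is sqrt(2/pi) = 0.798. Without selection it is sqrt(2/pi)/sqrt(6) = 0.326.
- At d > 0, the mean given six positive changes is d + phi(d)/Phi(d). For d = 0.5 this is 0.5 + 0.509 = 1.009. Allowing for the rare all-negative sets lowers it to 0.996.

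The loose-reading means come from a simulation of 2,000,000 trials per effect size.

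| True change (SD) | Chance reported, strict | Mean reported, strict | Chance reported, loose | Mean reported, loose |
|---|---|---|---|---|
| 0 (absolute change) | 0.031 | 0.80 | 0.219 | 0.57 |
| 0.5 | 0.110 | 1.00 | 0.414 | 0.77 |
| 1 | 0.355 | 1.29 | 0.757 | 1.13 |
| 2 | 0.871 | 2.06 | 0.993 | 2.01 |

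The first row uses absolute change because both rules are symmetric, so the signed bias at the null is zero.

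**Unlisted endpoints.** With k independent null endpoints, the chance that at least one passes the strict rule is 1 - (1 - 0.03125)^k: 0.147 for k = 5, 0.272 for k = 10 and 0.470 for k = 20. The documents do not give k.

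**Fewer than six pairs.** With five pairs the smallest two-sided p is 2/32 = 0.0625. The strict reading would then pass no paired test, and the strict columns would not apply.

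**The case against.** Several objections have force. The endpoints are exploratory, the rule is disclosed in advance in both documents, and the main objectives are outside it. Both definitions used in the illustration are mine, and a clear null could also be judged meaningful. Six pairs is the ceiling, because Part 2 enrols up to 6 and leukapheresis is optional. SAP 4.9.3 itself warns that data may be non-normal or censored. The table lists and shells are in a programming plan, and the publication terms in a site agreement, that are not part of these documents. All of this limits the size of the problem. None of it supplies a definition or makes the rule independent of the result.

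A reader might infer more than the text supports:

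- **That the rule contradicts SAP 4.9.1 and Protocol 14.5.1.** The sentence there, "Results will be presented as the proportion with decreased IUPM and the corresponding confidence interval (CI", sets a summary format and names neither the CSR nor the lock. SAP 4.9 makes the SAP analyses optional. Protocol 14.5.1 has no enrolment condition, but it names no report either. The 5 of 6 row belongs to a table of precision calculations and does not promise to report such a result.
- **That T-cell phenotype falls under two conflicting rules.** SAP 4.11 says that summary statistics for the Protocol 10.3 biomarkers "and corresponding changes from baseline, will be summarized and may also be presented graphically". Neither document assigns T-cell phenotype by name to an exploratory objective, so the second rule would be the reader's own mapping.
- **That omission is mandatory.** SAP 4.9 uses the same construction beside the word optional, and permission is the natural reading in both places.

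SAP 5 might be offered as a cure. The sections it cites cover populations, demographics and exposure, so the reference looks misnumbered. Whatever was meant, it makes no commitment to report exploratory results.

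**Conclusion.** The concern holds as a permission to report selectively. SAP 2.3 and Protocol 3.3 let exploratory results be left out of the CSR or the lock according to an undefined judgement of what they show, and no other section cures this. The rule differs in kind from the enrolment condition in SAP 4.9 and fits poorly with Protocol 14.11. The documents do not support calling it a contradiction of the QVOA sections.

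The size cannot be fixed from the documents. Under the stated assumptions, the distortion is large for null and small effects and negligible at the 2 SD effect used for the plan's power statement. It shrinks under the looser definition, and also to the extent that the permission is not used. The safety, PK, ADA and cytokine conclusions do not change. The point should be corrected because the exploratory virologic and immunologic results are the ones at risk and the correction is cheap.

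**What to change.** Delete "unless they represent meaningful findings" in Protocol 3.3 and the same clause in SAP 2.3. Replace the sentence with one to this effect: *Every exploratory analysis performed will be locked, in the main lock or a later dated one, and reported in the CSR or a dated addendum whatever its result, with the number of endpoints analysed. Deferral will depend only on assay completion.*

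Align SAP 4.9 at the same time. The only ground for not performing the tests should be the prespecified enrolment condition, with individual data listed in that case. Without this edit the new commitment and the SAP 4.9 opt-out could conflict when fewer than 6 participants enrol.

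The cost is small: one sentence in each document, the SAP 4.9 edit, and a minor protocol amendment through the sponsor, DAIDS and IRB route in Protocol 16.1. Protocol 9.16 sends assays to several laboratories, so a later lock may be needed. The downside is a few extra listings or an addendum. No sample size, significance level or power figure changes.
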